6.1.1 Clinical Laboratory Tests

Lab data collected centrally by UCSF and by local labs will be summarized. Normal ranges will be used to identify values that are outside the normal ranges and abnormal laboratory results will be graded according to the NCI-CTCAE Version 4.03.

Descriptive statistics will be provided for each test result and for the change from baseline by visit. A shift summary of baseline grade by maximum post baseline NCI-CTCAE toxicity grade will be presented, as appropriate for selected parameters. For each laboratory parameter, the baseline laboratory value will be defined as the last laboratory value collected on or prior to the date of the first dose of study drug. A listing of subjects who develop toxicities of Grade ≥ 3 will be provided for each lab type. Liver function test data will be summarized based on eDISH and Hy's Law criteria [11]. Listings will be provided for subjects who meet the eDISH criteria and Hy's Law criteria, respectively.

6.1.2 Vital Signs

Each vital sign (temperature, blood pressure (systolic and diastolic), respiration rate, and heart rate) and change from baseline for blood pressure will be summarized and presented by treatment group and study visit. Subjects with clinically significant abnormalities in vital signs as compared to baseline will be listed.

Data will be summarized and presented according to the following categories:

Parameter		Criteria for Clinically Significant Abnormality
Systolic Pressure	Blood	Absolute result > 160 mmHg and increase from baseline > 20 mmHg
		Absolute result < 90 mmHg and decrease from baseline > 20 mmHg
Diastolic Pressure	Blood	Absolute result > 100 mmHg and increase from baseline > 10 mmHg
		Absolute result < 50 mmHg and decrease from baseline > 10 mmHg
Weight		5 - < 10% weight loss from baseline
		10 - < 20% weight loss from baseline
		\geq 20% weight loss from baseline

6.1.3 Electrocardiogram

Electrocardiograms (ECGs) (12-lead) will be recorded at Screening. Abnormalities noted at screening will be included in the medical history.

ARN

7. PHARMACOKINETICS

Pharmacokinetic assessment (trough PK samples) will be performed per protocol.

8. BIOMARKERS

Biomarker analyses will be conducted on archival FFPE blocks or slides, plasma and whole blood samples collected from subjects who consented to participate in biomarker analysis to assess AR^{F876L} mutation and other resistance markers from all 3 treatment groups.

Further association may be made with clinical endpoints with:

- Markers identified from RNAseq analysis of archival tumor samples
- Plasma DNA at progression or end of treatment will be used to assess the frequency of AR^{F876L} mutation
- Whole blood samples collected at baseline and end of treatment or progression will be used to identify the type and frequency of AR anomalies or other RNA based markers associated with apalutamide treatment resistance or response

The association of the rest of the biomarkers with clinical response or relevant survival endpoints may be assessed using appropriate statistical methods (eg, analysis of variance [ANOVA], categorical or survival models), depending on the endpoints. Analyses may be performed within and between each treatment group. Other clinical covariates (such as baseline tumor characteristics and subject demographics) may also be included in the model. Correlation of baseline biomarker expression levels with clinical response or relevant time-to-event endpoints may be performed to identify responsive (or resistant) subgroups.

Biomarker analyses are dependent upon the availability of appropriate biomarker assays and adequate subject material. Therefore, some analyses may be deferred or not done if, for any reason, the analysis will have no scientific value. Biomarker data from this study may be compared with or combined with data obtained from prior studies.

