In summary, the proposed trial will evaluate the effects of 12 months of therapy with a highly potent AR inhibitor (ARN-509) alone, or in combination with an LHRHa, each compared with LHRHa alone on a number of short-term markers, including quality of life, metabolic parameters, and PSA modulation. The anticipated results from this trial may provide justification for larger definitive trials of second generation AR inhibitors as a treatment alternative to LHRHa monotherapy in patients with BCR.

6.4.2.4 Correlative studies: Exploratory Biomarkers:

- For consenting subjects, archived tumor samples FFPE blocks or slides will be collected any time after enrollment to gain understanding of biology and identify markers associated with response or resistance to complete androgen annihilation compared with apalutamide or LHRH alone
- For consenting subjects whole blood will be collected at baseline (predose on Day 1 of study treatment) and end of treatment or progression in PAXgene tubes for RNA testing for markers previously demonstrated to confer resistance to ARN-509 (see Section 7.1).

These include androgen receptor anomalies (eg: AR amplification, ARv3/7, and ARv567), AR axis genes, and other compensatory pathway markers.

- Previous studies with metastatic CPRC subjects provide evidence that an acquired mutation in the androgen receptor (AR^{F876L}) may be associated with resistance to ARN-509 treatment [60]. Plasma-based circulating DNA will be used to assess the presence of the AR^{F876L} mutation at progression

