2.2.1 Day 1 of Study Treatment

Patients will return to study site for a history and physical exam including weight, measurement of serum PSA, and dispensing of study drug(s), including the first injection of LHRHa and 1-month supply of apalutamide for subjects randomized to those arms. Collection of optional samples (samples for banking, archival FFPE blocks or slides for transcriptome profiling (RNAseq), whole blood for RNA testing, and plasma for biomarker testing) should occur before pre-dose.

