5.1 Analysis Specification

5.1.1 Level of Significance

In general, a two-sided significance level of $\alpha = 0.05$ will be used for all hypothesis testing and all CIs will be calculated on the two-sided 95% confidence level, unless otherwise specified. Since this is a three-arm study testing two simultaneous hypotheses, $\alpha/2 = 0.025$ level of significance will be used to test each.

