5.3.1.3 Metabolic and Hormonal Parameters

The mean change from baseline for markers of insulin resistance (including fasting glucose, insulin, body mass index, and hemoglobin A1C), fasting lipid panel (including total cholesterol, LDL, HDL, and serum triglycerides), and hormone levels (including DHT and estradiol) analyzed using a similar approach as for the primary endpoint.

The mean change in bone mineral density at the femoral neck, and lumbar spine as measured by DEXA scan will be compared for apalutamide monotherapy vs. LHRHa monotherapy and apalutamide + LHRHa vs. LHRHa monotherapy using an analysis of covariance that controls for baseline values of the corresponding measurement.

The time to serum testosterone recovery to > 50 ng/dL and > 150 ng/dL after the cessation of protocol therapy at 12 months will be compared for apalutamide + LHRHa vs. LHRHa monotherapy. The probability distributions by treatment group of the time to testosterone recovery will be estimated using the Kaplan-Meier method. The log-rank test will be used to compare the distribution of time to testosterone recovery. Subjects who discontinue study drug prior to 12 months for disease progression, unacceptable toxicity, or study withdrawal, as well as subjects who continue hormonal therapy after 12 months or receive non-protocol therapy, will not be included in the analysis of this exploratory endpoint.

No adjustment for multiple comparisons will be made for the analysis of the secondary and correlative endpoints.

Table 1: Key censoring rules

Scenario	Censoring rule
Time to PSA Progression	
 Any increase in PSA to $> 50\%$ of the baseline value or an increase of ≥ 2 ng/mL above the nadir, whichever is higher, and confirmed by repeat measurement at least 2 weeks later is considered an event. Subjects who have no PSA progression at the time of analysis will be censored at the last known date of PSA assessment. Subjects without a baseline PSA or without any post baseline values will be censored at randomization date.

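### The RNAseq marker search in SAP 8 has no false discovery control, and the only multiplicity rule that reaches it is no adjustment

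*SAP*

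**What the plan says.** SAP 2.2.1 and Protocol 7.5.1 describe the optional archival tumor samples as material for transcriptome profiling by RNAseq. Protocol 6.4.2.4 gives the purpose: to "identify markers associated with response or resistance to complete androgen annihilation compared with apalutamide or LHRH alone". SAP 8 says that clinical endpoints may then be associated with "Markers identified from RNAseq analysis of archival tumor samples". It allows analyses within and between treatment groups, leaves the choice of method open, and states neither a selection threshold nor a multiplicity procedure.

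Two general rules bear on this:

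- SAP 5.3.1.3, and Protocol 11.4.2 in the same words: "No adjustment for multiple comparisons will be made for the analysis of the secondary and correlative endpoints".
- SAP 5.1.1: in general, a two-sided level of 0.05 "will be used for all hypothesis testing and all CIs will be calculated on the two-sided 95% confidence level, unless otherwise specified". The level is halved to 0.025 only for the two main hypotheses, with the reason given as "Since this is a three-arm study testing two simultaneous hypotheses".

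**The concern.** The product of a discovery screen is a list of markers, and the list can be interpreted only if the reader knows roughly what share of it is expected to be chance. Leaving a handful of clinical secondary endpoints unadjusted is an ordinary phase 2 choice. The same rule carried over to a transcriptome puts no limit on the number of false hits. Effect sizes for markers that are selected and tested in the same men would also be biased away from zero. At stake is whether the archival tissue work can do what it was added to do, in at most about 90 men and probably fewer, since sampling is optional.

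**Working it through.** **Does the no-adjustment rule reach the RNAseq search?** The documents do not say so in terms. Read side by side, they point that way:

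- The archival tissue work is described in the Protocol under the heading "6.4.2.4 Correlative studies: Exploratory Biomarkers".
- Protocol 2.3.2 lists biomarker analysis of archival tissue among the secondary objectives. SAP 1.1.3 moves biomarker analyses to other objectives. In the Protocol the work falls under the sentence whether it is read as secondary or as correlative.
- In Protocol 11.4.2 the no-adjustment sentence is followed at once by a caveat that some correlative analyses may be deferred or dropped. The biomarker text there and SAP 8 repeat that caveat for biomarker analyses, so correlative appears to mean the biomarker work.
- Against this, SAP 5.3.2 lists only two correlative endpoints: the frequency of the AR F876L mutation and the frequency of known RNA resistance markers. Archival RNAseq is not listed.

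The reading is reasonable, but it is an inference. If it is rejected, SAP 8 has no multiplicity rule at all.

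**Inputs.** The level of 0.05 is the SAP 5.1.1 default. The planned sample is 90 men, 30 per arm (SAP 1.2). The number of transcripts G, the number or share of true markers, and the power per marker are not in the documents and are assumed below. The plan states no error rate for this search, so there is no figure to reproduce. Its one multiplicity calculation, 0.05/2 = 0.025 for the two main hypotheses, is correct.

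**False hits when nothing is associated:** 0.05 × G.

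- G = 10,000: 0.05 × 10,000 = 500
- G = 25,000: 0.05 × 25,000 = 1,250

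These are expected counts for each endpoint and each comparison. They do not require the tests to be independent.

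**False share with a fixed number T of true markers at 80% power:** FP = 0.05 × (G − T), TP = 0.8 × T, share = FP/(FP + TP), using expected counts.

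| G | T | FP | TP | False share |
|---|---|---|---|---|
| 10,000 | 50 | 497.5 | 40 | 497.5/537.5 = 93% |
| 25,000 | 50 | 1,247.5 | 40 | 1,247.5/1,287.5 = 97% |
| 10,000 | 200 | 490 | 160 | 490/650 = 75% |
| 25,000 | 200 | 1,240 | 160 | 1,240/1,400 = 89% |

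**False share by proportion π of true markers:** 0.05(1 − π) / [0.05(1 − π) + power × π]. Once π is fixed, G drops out.

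| π | Power 20% | Power 80% |
|---|---|---|
| 1% | 96% | 86% |
| 5% | 83% | 54% |
| 10% | 0.045/0.065 = 69% | 0.045/0.125 = 36% |
| 20% | 0.04/0.08 = 50% | 0.04/0.20 = 20% |

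Setting the share to 90% and solving for π gives 2.7% at 20% power, 1.1% at 50% and 0.7% at 80%. Nine in ten hits are false only when true markers are rarer than that.

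**Is 80% power realistic?** By the Fisher z approximation, 30 men give 81% power at two-sided 0.05 for a true correlation of 0.5, and 36% for 0.3. Within one arm, then, 80% is generous, and lower power raises the false share.

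**The case against.** The best reply is that the plan is silent rather than wrong. SAP 5.1.1 states 0.05 only as a general default that other text may override, and it sits in the efficacy section. SAP 8 leaves the method open and makes the associations optional. Nothing says that each transcript is tested at 0.05, or that passing 0.05 makes a marker identified. The work is labelled exploratory, may be deferred or not done, and may be compared or combined with data from prior studies. Under Protocol 15.6, exploratory biomarker results produced after the study report go into a separate report.

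Most of this stands, and it limits the point. A reader might infer that the plan expressly commits to an unadjusted gene-by-gene screen at 0.05, and that nearly all markers it yields would be false. The documents support neither reading. The first turns a default and an inference into a stated procedure. The second needs true markers to be about 1-3% of transcripts or fewer, and the documents give no such share.

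What the reply does not remove is that the only multiplicity rule that reaches this work is unsuited to a transcriptome-wide search, and SAP 8 puts nothing in its place. An exploratory label does not supply an error rate. The option to combine data with prior studies is not a commitment to validate.

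**Conclusion.** The point holds in a conditional form. The no-adjustment rule reasonably covers the RNAseq search, and SAP 8 adds no threshold or false discovery control. If transcripts were screened singly at the 0.05 default, the expected number of false hits would be large under any plausible transcript count. Their share of the list could be high or moderate: 75-97% with 50 to 200 true markers among 10,000 to 25,000 at 80% power, and 20-69% if 10-20% are true, over 20-80% power. Transcript count, number of true markers and power are all assumptions. The consequence is confined to exploratory biomarker conclusions. The primary, clinical secondary and safety results do not depend on it.

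**What to change.** - In SAP 5.3.1.3 and Protocol 11.4.2, exempt the archival-tumor RNAseq search from the no-adjustment sentence. Leave the sentence in force for the clinical secondary endpoints and for the two marker-frequency endpoints in SAP 5.3.2. The AR candidates named in Protocol 6.4.2.4 are measured in whole-blood RNA, a different specimen, and should not be folded into this change.
- In SAP 8, apply false discovery rate control over all transcripts tested for each endpoint and comparison, and report q-values. Benjamini-Hochberg at q ≤ 0.10 is one example. Under its usual dependence conditions it holds the expected false share at or below 10%.
- Label effect sizes of markers selected and tested in the same men as exploratory and in need of external confirmation.

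False discovery control suits discovery better than family-wise control here. With an assumed 20,000 transcripts, Bonferroni needs 0.05/20,000 = 0.0000025 per test. Power for a true correlation of 0.5 then falls from 99.9% to about 66% with all 90 men, and from 81% to about 3% with 30.

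The cost is a few sentences and a standard procedure, with no added patients, samples or visits. The downside is fewer nominal hits.

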9. MEDICAL RESOURCE UTILIZATION

Medical resource utilization will be descriptively summarized by treatment group. This report will be prepared separately and will not be a part of the clinical study report.

